2.3. Study Design

This is a Phase 1/2 substudy to describe the safety, tolerability, and immunogenicity of IRV (qIRV, tIRV, or bIRV) when administered in combination with bivalent BNT162b2 (original/Omi BA.4/BA.5). Bivalent BNT162b2 (original/Omi BA.4/BA.5) will be used during the substudy, as detailed in Table 7. Substudy B will be single-blind (sponsor unblinded). In Substudy B, up to approximately 630 participants 18 through 64 years of age will be enrolled.

Randomization will be conducted across 3 enrollment cohorts independently due to licensed QIV availability, with enrollment in these cohorts being conducted either concurrently or at different times as required based on operational considerations as shown in Table 2.

Table 2. Substudy B: Enrollment Cohorts

Enrollment Cohort	Total Number of	Number of Participants	Vaccine Group	Vaccine Group Descriptions
Conort	Participants	per Vaccine Group	Number	
1	60	30	1	Licensed QIV (Flucelvax) administered
1	00	30		concurrently in the opposite arm to BNT162b2 (original*/Omi BA.4/BA.5)
			2	Licensed QIV (Flucelvax) administered
				concurrently in the opposite arm to bIRV/bivalent
				BNT162b2 (original/Omi BA.4/BA.5)
2	360	Up to 120	3	qIRV/bivalent BNT162b2 (original/
		-		Omi BA.4/BA.5) at dose-level combination 1 ^a
			4	qIRV/bivalent BNT162b2 (original/
				Omi BA.4/BA.5) at dose-level combination 2 ^a
			5	qIRV/bivalent BNT162b2
				(original/Omi BA.4/BA.5) at dose-level
				combination 3 ^a
3	210	30	6	qIRV/bivalent BNT162b2 (original/
				Omi BA.4/BA.5) at dose-level combination 4 ^a
			7	qIRV/bivalent BNT162b2 (original/
				Omi BA.4/BA.5) at dose-level combination 5 ^a
			8	qIRV/bivalent BNT162b2 (original/
				Omi BA.4/BA.5) at dose-level combination 6 ^a
			9	qIRV/bivalent BNT162b2 (original/
				Omi BA.4/BA.5) at dose-level combination 7 ^a
			10	qIRV/bivalent BNT162b2 (original/
				Omi BA.4/BA.5) at dose-level combination 8 ^a
			11	tIRV/bivalent BNT162b2
				(original/Omi BA.4/BA.5)
			12	qIRV

a. Note: Combinations as shown in Table 7.

Note: * Original refers to the ancestral strain (Wuhan-Hu-1; USA-WA1/2020), also referred to in the protocol as the reference strain.

All participants will be asked to complete a reactogenicity e-diary for 7 days following vaccination.

Blood samples will be collected for immunogenicity assessments prior to vaccination and at 4 weeks after vaccination in Substudy B.

Following vaccination, AEs will be collected from informed consent signing through 4 weeks following vaccination, and SAEs will be collected from informed consent signing through 6 months after vaccination. In addition, AEs will be collected that occur up to 48 hours after blood draws.

3. ENDPOINTS AND BASELINE VARIABLES: DEFINITIONS AND CONVENTIONS

3.1. Primary Endpoints

- Abnormal troponin I laboratory values 2 days and 1 week after vaccination.
- New ECG abnormalities 2 days and 1 week after vaccination.
- Local reactions for up to 7 days following vaccination.
- Systemic events for up to 7 days following vaccination.
- AEs from vaccination through 4 weeks after vaccination.
- SAEs from vaccination through 6 months after vaccination.

3.1.1. Local Reactions and Systemic Events

Local reactions will be assessed at the injection site on the right arm only. Endpoints include both each reaction or event and any reaction or event.

The local reactions, including redness, swelling, and pain at the injection site, and the systemic events, including fever, fatigue (tiredness), headache, muscle pain, vomiting, diarrhea, chills, and joint pain, are reported in the e-diary from Day 1 through Day 7 after vaccination, where Day 1 is the day of vaccination. The e-diary entries from the participant will be the primary data source for these events. However, any related events that are considered local reactions or systemic events starting within 7 days after vaccination, that are recorded in the unplanned CRF or AE CRF, will be consolidated with e-diary data and the data included in the reactogenicity summaries if the participant has any e-diary data recorded.

This section describes derivations with details for the assessment of the reactogenicity data: severity level, duration, and onset day.

Severity and Maximum Severity

The definitions for reactogenicity severity collected from the e-diary and from AEs are described in Appendix 2.

For each local reaction or systemic event after vaccination, the maximum severity will be derived for the collection period (Day 1 through Day 7, where Day 1 is the day of vaccination) as follows:

maximum severity = highest grade (maximum severity) within 7 days after vaccination (Day 1 through Day 7) among severity grades reported for that local reaction or systemic event

Duration (First to Last Day Reported)

The duration (days) of each local reaction or systemic event will be calculated as the number of days from the start of the first reported reaction or event to the resolution of the last reported reaction or event, inclusive. For reactions or events collected in the e-diary, resolution is defined as the last day on which the reaction or event is recorded in the e-diary if the reaction or event lasted 7 days or less, or it is defined as the day on which the reaction or event ended beyond Day 7 (the latter will be collected on the CRF). For reactions and events collected in the AE CRF, the AE end date will be considered the resolution date. For a reaction or event collected in multiple sources, the latest date will be used in calculating the duration. If there is no known resolution/end date, the duration will be reported as unknown or missing.

Onset Day

The onset day of each local reaction or systemic event will be derived. Onset day is defined as the first day of reporting the reaction or event with any severity after study intervention administration. For a reaction or event collected in multiple sources, the earliest reported date of the reaction will be used in calculating the onset day.

Presence will be derived for each day and any day.

Use of Antipyretic/Pain Medication

The use of antipyretic/pain medication is also recorded in the e-diary from Day 1 through Day 7, where Day 1 is the day of vaccination. For the use of antipyretic/pain medication from Day 1 through Day 7, the following endpoint and variable will be derived:

• Presence (yes or no) of use of antipyretic/pain medication after vaccination (on any day and for each day).

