10.12.6.2.2. Blinding of Site Personnel for Substudy B

Substudy B is single-blind, such that all site personnel, including the investigator, investigator staff, and study staff receiving, storing, dispensing, preparing, and administering the study interventions will be unblinded.

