10.12.9.1.1. Estimands for Substudy B

10.12.9.1.1.1. Primary Estimands/Coprimary Estimands for Substudy B

The estimands to evaluate the safety objective are based on the safety population. These estimands estimate vaccine safety after study intervention. Completely missing e-diary data will not be imputed; missing AE dates and missing AE intensity will be handled according to Pfizer safety rules. Missing e-diary data not recorded in the e-diary will be recorded on the AE CRF. Therefore, the primary analysis will use reactogenicity recorded as AEs in the CRF to impute the missing e-diary data.

10.12.9.1.1.2. Secondary Estimands for Substudy B

The secondary estimands corresponding to each secondary objective are described in the table in Section 10.12.3.

The estimands to evaluate the immunogenicity objectives are based on the evaluable immunogenicity population. These estimands estimate the immune response after study intervention administration in the hypothetical setting where participants follow the study schedules and protocol requirements as directed. Missing immunogenicity results will not be imputed, as MCAR is assumed. For participants who discontinue from the study or have major protocol violations, all postdiscontinuation or postviolation observations will be censored.

Immunogenicity results that are below the LLOQ will be set to $0.5 \times LLOQ$ in the analyses.

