5.3. Methods to Manage Missing Data

Standard algorithms on handling missing AE dates will be applied according to Pfizer safety rules. A completely missing start date for an AE is not allowed in data collection. For derived variables based on reactogenicity data, if any day of the 7-day e-diary is available, the "any day (Day 1 through Day 7)" data will be considered nonmissing. It is expected that these reactogenicity events would be queried by the investigator for the missing e-diary days and would be entered in the AE CRF if any reactogenicity was not reported in the e-diary due to missed days. Therefore, the primary analysis will use the reactogenicity recorded in the AE CRF to impute the partially missing e-diary data to estimate the reactogenicity rate during the e-diary collection period. The AE CRF is designed as a log page, which means only events that occurred will be recorded and events that did not occur will not be recorded. Therefore, all remaining missing days are considered as having answered "no." This imputation can reasonably estimate the reactogenicity event rates during the e-diary collection period.

Antibody titers below the LLOQ, denoted as BLQ, or below the LOD will be set to $0.5 \times \text{LLOQ}$ for GMT analysis. No other missing assay data will be imputed in the analyses.

When calculating a fold rise, the assay results will be converted to $0.5 \times LLOQ$ if assay results are < LLOQ, except when the prevaccination assay result is < LLOQ while the postvaccination result is $\ge LLOQ$, in which case the prevaccination value will be set to LLOQ. If both the numerator and denominator are < LLOQ, then both will be converted in the same way.

Values for sera that are insufficient, indeterminate results, or values recorded as "not done" will be set to "missing."

LLOQs for each assay used in this study will be included in serology data transfer once they are available.

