6.1.2.2. Sensitivity/Supplementary Analysis

The proportion of participants reporting AEs (which includes reactogenicity events collected in the AE CRF during the e-diary collection period) from vaccination through 4 weeks after vaccination will be provided as a sensitivity analysis.

Additional analyses will include summaries of AE/SAEs by SOC and PT. Furthermore, descriptive summaries may be done for different types of AEs (eg, related AEs, severe AEs, immediate AEs, AEs leading to discontinuations, etc). Additionally, any AEs occurring up to 48 hours after the blood draws at the 4-week follow-up visit will be summarized descriptively or included in the listing.

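### Substudy B SAP 3.1.1 merges only 'related' CRF events into reactogenicity; read as causality, this conflicts with SAP 5.3 and the protocol and can turn a recorded event into a 'no'

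*SAP*

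**What the plan says.** The primary reactogenicity endpoint in Substudy B is the percentage of participants reporting each local reaction or systemic event within 7 days. Four parts of the plan govern how CRF records enter it.

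- **Substudy B SAP 3.1.1.** On the diary: "The e-diary entries from the participant will be the primary data source for these events". CRF records from the unplanned-visit page or the AE page are then consolidated, but the text admits "any related events that are considered local reactions or systemic events starting within 7 days after vaccination", and only "if the participant has any e-diary data recorded". The word *related* is not defined there.
- **Substudy B SAP 5.3.** Here "the primary analysis will use the reactogenicity recorded in the AE CRF to impute the partially missing e-diary data". Days still missing after that step count as 'no'.
- **Protocol 10.12.9.1.1.1**, repeated in substance in 9.3.1: "the primary analysis will use reactogenicity recorded as AEs in the CRF to impute the missing e-diary data". Protocol 8.3.5 requires a prompted reaction from a missed diary entry to go on the AE CRF, whatever its cause.
- **Protocol 10.12.6.2.2.** On blinding, "all site personnel, including the investigator, investigator staff, and study staff receiving, storing, dispensing, preparing, and administering the study interventions will be unblinded".

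Substudy B SAP 2.1 declares no modification of the protocol's analysis plan.

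**The concern.** The e-diary asks whether a prompted symptom was present and how severe it was. It does not ask why, so a diary 'yes' for headache counts even if the participant had a cold. If CRF events must first be judged causally related, the same endpoint follows two rules depending on where the event was written down. The second rule rests on a judgement made by someone who knows the vaccine group.

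What is at stake is a limited part of the primary safety summary: events on missed diary days, grades that are higher on the CRF than in the diary, and onset or resolution dates taken from the CRF. Grade 4 deserves most attention, because Appendix 2 of the Substudy B SAP says that Grade 4 reactions are collected as AEs on the CRF and not through the diary.

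**Working it through.** The plan states no figure for this point, so there is none to reproduce. The check compares the passages, traces records through the rules, and then gives the effect per participant.

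**1. Does any other statement of the rule carry a causality condition?**

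| Source | Which CRF events are used | Causality condition |
|---|---|---|
| Substudy B SAP 3.1.1 | *related* events considered local reactions or systemic events | yes, if *related* is causal |
| Substudy B SAP 5.3 | reactogenicity recorded in the AE CRF | none |
| Protocol 9.3.1 and 10.12.9.1.1.1 | reactogenicity recorded as AEs | none |
| Protocol 8.3.5 (what sites must enter) | any prompted event from a missed entry | none |

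**2. What does *related* mean in 3.1.1?**

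For causality:
- Section 6.1.2.2 of the same SAP lists related AEs as a type of AE.
- Protocol 10.3.3 requires the investigator to assess the relationship for every AE.
- If *related* meant only a match on terms, it would repeat what the rest of the phrase already says.

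For term matching:
- The SAP's version history describes this change as covering AEs that correspond to reactogenicity terms.
- The unplanned-visit assessments listed in protocol 10.12.8.9.7, whose CRF page is the other source named in 3.1.1, include no causality call.

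The causal sense is the more natural one for a programmer, but the text does not settle it.

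**3. Three participants with a headache on Day 3 only, and e-diary data on other days**

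| Participant | Day 3 record | Causal reading | Term-matching reading |
|---|---|---|---|
| A | e-diary | yes | yes |
| B | AE CRF, judged related | yes | yes |
| C | AE CRF, judged not related | **no** | yes |

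On the causal reading, C's event is not merged, Day 3 stays missing, and 5.3 turns it into 'no'. C remains in the denominator, because 6.1.1.1 counts everyone with any reactogenicity data. Had C also reported headache in the diary on another day, C would score 'yes' on either reading.

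**4. Severity and dates.** Appendix 2 takes the highest grade across sources. Section 3.1.1 takes the earliest date for onset and the latest for resolution. If a CRF record is filtered out, its grade and dates go with it.

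**5. Effect per participant.** With *k* affected participants in a group of *n*, the rate falls by 100 × *k*/*n* points. The documents do not give *k*, or the rates of missed diary days, CRF-only events or not-related calls that would produce it. The counts below are therefore illustrations, with exact Clopper-Pearson 95% intervals.

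- *n* = 30: 1/30 = 3.3 points each. 2/30 = 6.7% (0.8 to 22.1) becomes 1/30 = 3.3% (0.1 to 17.2) with *k* = 1, or 0/30 = 0% (0 to 11.6) with *k* = 2. For a common event, 18/30 = 60.0% (40.6 to 77.3) becomes 16/30 = 53.3% (34.3 to 71.7) with *k* = 2.
- *n* = 120: 1/120 = 0.8 points each. 1/120 = 0.8% (0.0 to 4.6) becomes 0/120 = 0% (0 to 3.0) with *k* = 1.

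For common events the shift is well inside the interval. For a rare or Grade 4 event, one participant can decide whether it appears in the table at all.

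**The case against.** The strongest reply is that *related* refers back to the diary events just named, so it means matching terms. The version history says as much, and on that reading 3.1.1, 5.3 and the protocol agree and nothing is lost. This stands as a possible reading. It does not remove the need for an edit, because the current sentence permits two different primary datasets and the wording of the version history would resolve it.

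A second reply is that the reach is small. That also stands. A reader might infer that the investigator's causality call decides whether any reaction counts. It does not: every diary entry counts, and only CRF-sourced information in participants with some diary data is exposed. Protocol 10.3.3 also treats an event of unknown cause as related for reporting purposes, which may reduce the number judged not related. The same section, however, requires evidence or argument for a relationship and not merely that one cannot be ruled out, so a not-related call for headache or fatigue remains plausible.

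A third reply is that Section 6.1.1.2 plans an analysis based only on e-diary data, which is free of any causality judgement. That helps show how much the CRF adds. It does not recover the events at issue, because it drops all CRF events.

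A reader might also infer that such an event disappears from the main AE analysis, because the sensitivity analysis in 6.1.2.2 is the one "which includes reactogenicity events collected in the AE CRF during the e-diary collection period". Section 6.1.2.1 states no exclusion, and a headache not treated as reactogenicity could simply remain an ordinary AE. The documents do not establish a double loss.

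**Conclusion.** The point holds in a conditional form. The word *related* in Substudy B SAP 3.1.1 is undefined. In its usual AE sense it adds a condition that SAP 5.3 and protocol 8.3.5, 9.3.1 and 10.12.9.1.1.1 do not contain, although SAP 2.1 declares no departure from the protocol. Applied that way, it would score an observed CRF-only event as absent on the judgement of an unblinded investigator, and could lower a maximum grade or alter a duration or onset day.

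The effect is 3.3 points per affected participant in a group of 30 and 0.8 points in a group of 120. The number affected cannot be derived from the documents.

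A reader might go further and infer a biased difference between the novel combinations and the licensed comparator. Unblinded judgement makes that conceivable. However, no document gives not-related rates by group, and the planned reactogenicity summaries are descriptive by group with no between-group comparison. No size for such a bias is supported.

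The conclusion rests on one assumption: that the programmer would take *related* as the causality flag.

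**What to change.** In Substudy B SAP 3.1.1, replace the limiting phrase with: any events corresponding to the prompted reactogenicity terms, regardless of investigator causality. Leave the 7-day window and the requirement for some e-diary data as they are. This brings 3.1.1 into line with 5.3, the protocol and the SAP's own version history. Causality can still be shown in the AE listings.

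If a causality filter is intended, the SAP should say so, reconcile 5.3 and the protocol sections with it, and add a reactogenicity analysis that ignores causality.

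The cost is one phrase and one check of the filter in the consolidation program, with no new data. The downside is that some reactogenicity rates may become slightly less favourable.

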10.12.6.1.1. Administration for Substudy B

See Section 6.1.1.

During Substudy B, participants will receive study intervention at Visit 201 as randomized in accordance with the SoA (Section 10.12.1). All study intervention should be administered intramuscularly into the deltoid muscle of the right arm, other than licensed QIV, which should be administered intramuscularly into the deltoid muscle of the left arm.

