- Ask the participant to contact the site staff or investigator immediately if he or she
 experiences any of the following from Day 1 through Day 7 after vaccination
 (where Day 1 is the day of vaccination) to determine if an unscheduled reactogenicity
 visit is required:
 - Fever ≥39.0°C (≥102.1°F).
 - Redness or swelling at the injection site measuring greater than 10 cm (>20 measuring device units).
 - Severe pain at the injection site.
 - Any severe systemic event.

- Record AEs as described in Section 8.4.1.
- Ask the participant to contact the site staff or investigator if a medically attended event (eg, doctor's visit, emergency room visit) or hospitalization occurs.
- Ask the participant to contact the site staff or investigator immediately if the participant experiences acute chest pain, shortness of breath, or palpitations (see Section 10.12.8.10).
- Schedule an appointment for the participant to return for the next study visit.
- Remind the participant to bring the e-diary to the next visit.
- Complete the source documents.
- The investigator or an authorized designee completes the CRFs and updates the study intervention accountability records.
- The investigator or appropriately qualified designee reviews the reactogenicity
 e-diary data online following vaccination to evaluate participant compliance and as part
 of the ongoing safety review. Daily review is optimal during the active diary period.

10.12.8.9.3. Visit 202 – Day 3 Follow-Up Visit (After Vaccination) – 2 to 4 Days After Visit 201 for Substudy B

- Record AEs as described in Section 8.4.1.
- Record nonstudy vaccinations as described in Section 10.12.6.7.
- Record prohibited medication use as described in Section 10.12.6.7.1.
- Verify understanding of and compliance with protocol requirements for contraception as described in Section 5.3.1.
- Review screening central laboratory results (troponin I) and central ECG reports. Any abnormal troponin I level must result in further assessments as outlined in Section 10.12.8.10.
- Perform 12-lead triplicate ECG. Any new ECG abnormality (compared to baseline) consistent with probable or possible myocarditis or pericarditis (as listed in Section 10.12.8.5.1) must result in further assessments as outlined in Section 10.12.8.10.
- Measure vital signs, including oral temperature, pulse rate, and seated blood pressure.

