Appendix 2. Reactogenicity Data Consolidation

For reactogenicity collected in the e-diary, redness and swelling will be measured and recorded in measuring device (caliper) units, and then categorized during analysis as mild, moderate, or severe based on the grading scale in Table 3. Measuring device units can be converted to centimeters according to the following scale: 1 measuring device unit = 0.5 cm. Pain at the injection site will be assessed by the participant as mild, moderate, or severe according to the grading scale in Table 3. The systemic events of fatigue (tiredness), headache, muscle pain, vomiting, diarrhea, chills, and joint pain will be assessed by participants as mild, moderate, or severe according to the grading scale in Table 4. Grade 4 reactions and events, which can only be classified by an investigator or medically qualified person, will be collected as AEs on the CRF. For reactogenicity collected in the AE CRF, the grading scales will be based on the AE intensity scale in Table 5. If a local reaction or systemic event is captured in more than 1 data source, eg, the e-diary, unplanned assessments, and/or AE CRF, the highest grade will be used in the safety summary analysis.

Table 3. Local Reaction Grading Scale

	Mild (Grade 1)	Moderate (Grade 2)	Severe (Grade 3)	Potentially Life-Threatening (Grade 4)
Pain at the injection site	Does not interfere with activity	Interferes with activity	Prevents daily activity	Emergency room visit or hospitalization for severe pain
Redness	>2.0 cm to 5.0 cm (5 to 10 measuring device units)	>5.0 cm to 10.0 cm (11 to 20 measuring device units)	>10 cm (≥21 measuring device units)	Necrosis or exfoliative dermatitis
Swelling	>2.0 cm to 5.0 cm (5 to 10 measuring device units)	>5.0 cm to 10.0 cm (11 to 20 measuring device units)	>10 cm (≥21 measuring device units)	Necrosis

Table 4. Systemic Event Grading Scale

	Mild (Grade 1)	Moderate (Grade 2)	Severe (Grade 3)	Potentially Life- Threatening (Grade 4)
Vomiting	1-2 times in 24 hours	>2 times in 24 hours	Requires IV hydration	Emergency room visit or hospitalization for hypotensive shock
Diarrhea	2 to 3 loose stools in 24 hours	4 to 5 loose stools in 24 hours	6 or more loose stools in 24 hours	Emergency room visit or hospitalization for severe diarrhea
Headache	Does not interfere with activity	Some interference with activity	Prevents daily routine activity	Emergency room visit or hospitalization for severe headache

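### The Substudy B SAP does not limit CRF-sourced local reactions to the right arm, so left-arm QIV reactions in Groups 1 and 2 can enter a right-arm primary endpoint

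*SAP*

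**What the plan says.** The endpoint is defined by arm. The objectives tables in protocol 10.12.3 and SAP (Substudy B) 2.2 both restrict local reactions to the right arm, and SAP 3.1.1 opens with "Local reactions will be assessed at the injection site on the right arm only". Protocol 8.3.5.2 limits the assessment of local reactions in the same way.

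The injections are also split by arm. Protocol 10.12.6.1.1 puts all study intervention in the right arm, "other than licensed QIV, which should be administered intramuscularly into the deltoid muscle of the left arm". Only Groups 1 and 2 receive QIV (protocol Table 8; SAP Table 2).

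SAP 3.1.1 makes the e-diary the primary source and then adds a second one. It takes "any related events that are considered local reactions or systemic events starting within 7 days after vaccination" and provides that those "that are recorded in the unplanned CRF or AE CRF, will be consolidated with e-diary data and the data included in the reactogenicity summaries". A further condition is that they are "included in the reactogenicity summaries if the participant has any e-diary data recorded". Section 5.3 says that the primary analysis uses reactogenicity on the AE CRF to fill partially missing diaries. Appendix 2 says that when a reaction is captured in more than one source, "the highest grade will be used in the safety summary analysis".

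Section 6.1.1.2 plans a supplementary analysis from diary data alone. Section 6.1.2.2 plans a sensitivity AE analysis "which includes reactogenicity events collected in the AE CRF during the e-diary collection period".

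**The concern.** The arm limit appears where the endpoint is defined, but not in the consolidation rule, the imputation rule or the highest-grade rule. For most groups this does not matter, because there is only one injection. In Groups 1 and 2 there is a second injection site, which the diary does not cover. A reaction at that site can reach the database only through CRF records, and those are the records that get merged.

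If left-arm events are merged, the primary local-reaction and severe-reaction rates in Groups 1 and 2 combine reactions to two vaccines at two sites. In Groups 3 to 12 they reflect one. Group 1 is the licensed-vaccine comparator and Group 2 is the only bIRV group, so their rates will naturally be read against the others.

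**Working it through.** The plan gives no figure for this point, so there is none to reproduce. The check compares the texts, follows one record through the rules, and then shows the scale.

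**1. Routes by which a left-arm reaction can reach a CRF**
- Acute reactions in the 30-minute observation go on the AE page (protocol 8.3 and 10.12.8.9.2). No arm is stated.
- Participants are told to call the site for events such as "Redness or swelling at the injection site measuring greater than 10 cm", so that the need for an unscheduled visit can be judged. No arm is stated.
- Unscheduled visits measure redness, swelling and pain (protocol 10.12.8.9.7). No arm is stated.
- A participant may also report a reaction spontaneously as an AE.

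**2. One illustrative record, Group 1**

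The right-arm diary is negative on all 7 days. The AE CRF holds moderate injection-site pain in the left arm, onset Day 2, judged related.
- Related: passes. Protocol Section 6 lists licensed QIV as a study intervention, so this condition does not remove QIV reactions.
- Considered a local reaction: injection-site pain is one of the three terms.
- Onset within 7 days: passes.
- Some diary data: passes.

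Taken literally, the merge scores this participant as having a moderate local reaction. If the opening sentence of 3.1.1 is carried over to CRF records, the score is none. The text permits both codings.

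**3. Who can be affected**

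Groups 1 and 2: 2 × 30 = 60. Total: 60 + 360 + 210 = 630. Share: 60/630 = 9.5%.

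**4. Scale in a group of 30**

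Each participant whose only local reaction is a merged left-arm event adds 1/30 = 3.3 percentage points. The starting counts and additions below are assumptions. The intervals are Clopper-Pearson 95%.

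| Assumed right-arm count | Added left-arm only | Reported rate (95% CI) |
|---|---|---|
| 15/30 | 0 | 50.0% (31.3–68.7) |
| 15/30 | 1 | 53.3% (34.3–71.7) |
| 15/30 | 3 | 60.0% (40.6–77.3) |
| 3/30 | 0 | 10.0% (2.1–26.5) |
| 3/30 | 1 | 13.3% (3.8–30.7) |
| 3/30 | 3 | 20.0% (7.7–38.6) |

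More generally, the added proportion is (1 − p) × q. Here p is the true right-arm rate, and q is the chance that a participant with no right-arm reaction has a merged left-arm record. Neither is in the documents. With p from 30% to 80% and q from 1% to 20%, both assumed, it runs from (1 − 0.8) × 0.01 = 0.2 points to (1 − 0.3) × 0.2 = 14 points. On the right-arm reading it is 0.

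**5. Which comparisons are touched**

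Groups 1 and 2 make up the whole of Cohort 1, and both receive QIV. The merge should therefore produce no systematic difference between them. It would show when either is set beside Groups 3 to 12, which are randomized in separate cohorts.

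**6. Does the diary-only analysis settle it?**

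CRF records cannot affect it, so a gap from the primary result would be visible. That gap would also contain legitimate right-arm reactions entered on the AE CRF for missed diary days (protocol 8.3.5), so the cause could not be isolated.

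**The case against.** The strongest reply is that 3.1.1 already supplies the limit. Its first sentence and both estimand tables say right arm only, a consolidation rule would not normally override its own endpoint definition, and nothing says that left-arm events count. This stands as far as it goes, and it may well be what was intended. But that sentence concerns how reactions are assessed. The merge sentence then brings in another source with its own list of conditions, and arm is not on the list.

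Other points also stand. The CRF is not available here and may already record the arm. The unscheduled-visit procedure is written around diary reports, which cover the right arm, although participant calls and acute reactions remain open. Safety in this substudy is descriptive, and the planned Group 1 comparisons in SAP 6.2.1.2 concern immunogenicity only.

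A reader might infer four stronger things that the documents do not support:
- That every CRF local reaction is merged. The rule is limited to related events, onset within 7 days and participants with some diary data.
- That left-arm reactions definitely are counted. The text allows it but does not say so.
- That the effect simply favours the combination vaccines over the comparator. Group 2 is itself an investigational combination, would be raised too, and is the only group randomized against Group 1.
- That filtered left-arm events vanish from both primary tables. Section 6.1.2.2 implies that the main AE analysis omits reactogenicity recorded on the AE CRF, but 6.1.2.1 states no such exclusion. On the right-arm reading, a left-arm event is an ordinary AE.

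**Conclusion.** The gap is real and narrow. The rules in SAP (Substudy B) 3.1.1, 5.3 and Appendix 2 lack the arm condition that defines the primary endpoint, so left-arm QIV reactions in Groups 1 and 2 can enter right-arm rates. At most 60 of 630 participants are involved. The one figure that needs no assumption about reaction rates is 3.3 points per affected participant in a group of 30, and a single severe left-arm event could move a severe rate by the same amount. The number of such participants is unknown and could be zero. The conclusion assumes that some left-arm reactions are recorded on a CRF as related, and that the programmer applies the merge rule as written. It is worth correcting because a primary endpoint should not admit two codings, and removing the ambiguity costs very little.

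**What to change.** In SAP (Substudy B) 3.1.1, 5.3 and Appendix 2, state that for local reactions the consolidation, the imputation of missed diary days and the maximum grade use only events at the right-arm injection site. Take the arm from the CRF if it is recorded there, otherwise from the AE verbatim term or a query. In 6.1.2, state that left-arm QIV injection-site events in Groups 1 and 2 are kept in the main AE analysis, so that they are reported whichever way the rules are read. Systemic events need no change, since they have no arm.

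The cost is a few sentences in the SAP and a site-of-injection check or query for AE records in up to 60 participants. No visit or new assessment is needed.
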